#### 6.3.9 Patients initiating dialysis during the treatment period

In patients judged on clinical grounds to require dialysis during the study, study medication should be continued until study closure, unless protocol specified reasons for investigational product discontinuation are present. Initiation of chronic dialysis should be recorded in the eCRF.

### 6.4 Reporting of serious adverse events

All SAEs have to be reported, whether or not considered causally related to the investigational product or to the study procedure(s). All SAEs will be recorded in the eCRF.

If any SAE occurs in the course of the study, then Investigators or other site personnel inform the appropriate AstraZeneca representatives within one day i.e. immediately but **no later than 24 hours** of when he or she becomes aware of it.

The designated AstraZeneca representative works with the Investigator to ensure that all the necessary information is provided **within 1 calendar day** of initial receipt for fatal and life threatening events **and within 5 calendar days** of initial receipt for all other SAEs.

For fatal or life-threatening adverse events where important or relevant information is missing, active follow-up is undertaken immediately. Investigators or other site personnel inform AstraZeneca representatives of any follow-up information on a previously reported SAE within one calendar day i.e. immediately but **no later than 24 hours** of when he or she becomes aware of it.

Once the Investigators or other site personnel indicate an AE is serious in the WBDC system, an automated email alert is sent to the designated AstraZeneca representative.

If the WBDC system is not available, then the Investigator or other study site personnel reports a SAE to the appropriate AstraZeneca representative by telephone. The AstraZeneca representative will advise the Investigator/study site personnel how to proceed. The reference document for definition of expectedness is the IB for the AstraZeneca drug.

## 6.5 Overdose

The maximum tolerated dose of roxadustat has not been established in humans. For the purposes of this study, exceeding the maximum allowed dose specified in this CSP (3.0 mg/kg or 300 mg per administration, whichever is lower) represents an overdose.

An overdose with associated AE(s) is recorded as the AE diagnosis/symptoms on the relevant AE modules in the eCRF and on the Overdose eCRF module.

An overdose without associated AE(s) is only reported on the Overdose eCRF module. If an overdose on an AstraZeneca study drug occurs in the course of the study, then the Investigator or other site personnel inform appropriate AstraZeneca representatives immediately or **no later than 24 hours** of when he or she becomes aware of it.

The designated AstraZeneca representative works with the Investigator to ensure that all relevant information is provided to AstraZeneca.

For overdoses associated with a SAE, the standard reporting timelines apply, see Section 6.4. For other overdoses, reporting must occur within 30 days.

## 6.6 Pregnancy

All pregnancies and outcomes of pregnancy should be reported to AstraZeneca or its representative on the pregnancy form.

### 6.6.1 Maternal exposure

If a patient becomes pregnant during the course of the study investigational product should be discontinued immediately.

Pregnancy itself is not regarded as an adverse event unless there is a suspicion that the investigational product under study may have interfered with the effectiveness of a contraceptive medication. Congenital abnormalities/birth defects and spontaneous miscarriages should be reported and handled as SAEs. Elective abortions without complications should not be handled as AEs. The outcome of all pregnancies (spontaneous miscarriage, elective termination, ectopic pregnancy, normal birth or congenital abnormality) should be followed up and documented even if the patient was discontinued from the study.

If any pregnancy occurs in the course of the study, then the Investigator or other site personnel informs the appropriate AstraZeneca representatives within 1 day i.e. immediately but **no later than 24 hours** of when he or she becomes aware of it.

The designated AstraZeneca representative works with the Investigator to ensure that all relevant information is provided within 1 or 5 calendar days for SAEs (see Section 6.4) and within 30 days for all other pregnancies.

The same timelines apply when outcome information is available.

### 6.6.2 Paternal exposure

Pregnancy of the patient's partners is not considered to be an adverse event. However, the outcome of all pregnancies (spontaneous miscarriage, elective termination, ectopic pregnancy, normal birth or congenital abnormality) should if possible be followed up and documented as described in Section 6.6.1. To capture information about a pregnancy from the partner of a male patient, the male patient's partner consent must be obtained to collect information related to the pregnancy and outcome; the male patient should not be asked to provide this information.

## 6.7 Management of IP related toxicities

Observed adverse effects demonstrated in nonclinical safety studies (refer to Section 4 of the IB) following administration of roxadustat are primarily caused by an exaggerated pharmacological response, which can be managed in the clinical setting. The dose algorithm will mitigate excessive Hb elevation.

If there are clinical concerns for a patient due to excessive elevation in Hb levels, the investigator may decide to perform a therapeutic phlebotomy instead of or in addition to, a dose hold. For overdose see Section 6.5.

## 6.8 Study governance and oversight

### 6.8.1 International coordinating investigator

The International coordinating investigator (ICI) in collaboration with AstraZeneca will be responsible for the overall design, interpretation, supervision and reporting (presented at international congresses and published in peer reviewed journals) of the study, including the development of the protocol and any protocol amendments.

### 6.8.2 Independent Endpoint Review Committee

An Independent Endpoint Review Committee (IERC) will be appointed and will adjudicate potential endpoint events. The committee members will not have access to individual treatment codes for any patient or clinical efficacy and safety event. The precise responsibilities and procedures applicable for the IERC will be detailed in a separate IERC charter.

### 6.8.3 Data Safety Monitoring Board

An independent Data Safety Monitoring Board (DSMB) will be appointed and will report to the International Coordinating Investigator and sponsor. The DSMB will be responsible for safeguarding the interests of the patients in the outcome study by assessing the safety of the intervention during the study and for reviewing the overall conduct of the clinical study. The DSMB will have access to the individual treatment codes and will be able to merge these with the collected study data while the study is ongoing.

The DSMB charter will be prepared to detail precise roles and responsibilities and procedures to ensure maintenance of the blinding and integrity of the study in the review of accumulating data and interactions with the International Coordinating Investigator and sponsor.

## 7. INVESTIGATIONAL PRODUCT AND OTHER TREATMENTS

### 7.1 Identity of investigational product(s)

**Table 3 Identity of investigational products**

Investigational product	Dosage form and strength	Manufacturer
Roxadustat	Oral tablets 20mg, 50mg and 100mg	FibroGen
Placebo	Oral tablets to match 20mg, 50mg and 100mg	FibroGen

The formulation number and batch number will be recorded in the study master file and identified in the clinical study report (CSR).

Roxadustat and matching placebo oral tablets will be packaged in bottles supplied by AstraZeneca. The tablet strengths are different in size and each strength has a matching placebo. The tablets should remain in original packaging until administration. The tablets

should be swallowed whole with water. The tablets must not be chewed, crushed or divided. The excipients include lactose monohydrate, microcrystalline cellulose, povidone, croscarmellose sodium, magnesium stearate and colorant Red Opadry II (contains Lecithin (Soya), FD&C Red #40 Aluminium Lake).

## **7.2 Dose and treatment regimens**

### **7.2.1 Randomization**

Patients will be randomized to receive roxadustat or placebo in a 1:1 ratio in a double-blind manner. Randomization schedules will be prospectively prepared. Automated randomization and assignment to treatment arm will be provided by IWRS/IVRS. The randomization in this study will be stratified by country.

The number of tablet bottles that will be dispensed may vary depending on the dose. Dispensation will be managed by IWRS/IVRS. The administration will be detailed on a dosing card. Doses administered will be recorded in the eCRF.

The administration of the first dose of study drug would mark the beginning of the treatment period. Hemocue values will be used for all dose adjustments, including baseline values from Hemocue values at randomization. Missed doses should not be replaced.

### **7.2.2 Starting dose and dose adjustment**

The initial study drug dose (per dose occasion) is 70 mg orally administered three times a week (TIW).

The first study drug administration will be on Day 1 (week 0). Study drug doses must be administered at least 2 days apart and no more than 4 days apart (e.g., Monday, Wednesday, Friday). Study drug will be dosed TIW throughout the study treatment period unless downward dose adjustment requires a change to twice or once weekly.

Dose adjustments are permitted starting at week 4 and at intervals of every 4 weeks until week 52, every 8 weeks thereafter using the dose adjustment algorithm (see [Table 4](#)). If dose reduction is required for excessive erythropoiesis, the dose may be adjusted at any time. All dose adjustments are based on Hb values using Hemocue, a point-of-care device. Hb values will be recorded in the eCRF (during the screening period) and in IWRS (during the treatment period).

**Table 4 Dose adjustment algorithm**

Changes in Hb over past 4 a weeks	Hb <10.5g/dL	Hb 10.5 to 11.9g/dL	Hb 12.0 to 12.9g/dL	Hb ≥13.0g/dL
<-1.0	↑	↑	No change	Hold, then resume dosing when Hb ≤11.9 g/dL, at a dose that is reduced by two dose steps
-1.0 to 1.0	↑	No change	↓	
>1.0	No change	↓	↓	

**Dose Increases and Reductions:**  
Dose increases (↑) and reductions (↓) are pre-set according to dose steps.  
The dose steps are as follows: 20, 40, 50, 70, 100, 150, 200, 250 and 300mg.  
*Example: A dose increase at a dose of 70 mg results in 100 mg as the new dose. A dose reduction at a dose of 150 mg results in 100 mg as the new dose.*  
If patients on 20 mg TIW need dose reduction, change frequency to twice a week, i.e. 20 mg administered twice a week. If further dose reduction is needed, reduce frequency to once weekly, i.e. 20 mg administered once a week.  
Note: Maximum dose is capped at the lower of 3.0 mg/kg or 300 mg per dose administration

**Dose Adjustment for Excessive erythroipoiesis**

- If Hb increases by >2.0 g/dL within a 4 week period, reduce dose by one step.

a After week 52, adjust dose based on current Hb (increase 1 dose step if <10.5g/dL, no change if 10.5 to 11.9 g/dL, decrease 1 dose step if 12 to 12.9 g/dL)

### 7.2.3 Dose adjustment for excessive Erythroipoiesis

Excessive erythroipoiesis is defined in Table 4. In the event of excessive erythroipoiesis, the dose may be adjusted at any time, even on visits without a dose adjustment review. In such cases, dose adjustment reviews are then resumed at 4-week intervals until week 52, where after there will be 8-week intervals. If a dose adjustment review is performed on week 18, then the next dose adjustment review will be scheduled on week 24, since there is no scheduled visit on week 22.

### 7.2.4 Dose adjustment for Hb ≥ 13.0g/dL

In the event of Hemocue Hb value ≥13.0g/dL, dosing will immediately be put on hold. Resume dosing at a subsequent visit when Hb ≤11.9 g/dL, at a dose that is reduced by two dose steps. After dosing has been resumed, the dose adjustment reviews are then continued at 4-week intervals until week 52, where after there will be 8-week intervals, following the same principle as for excessive erythroipoiesis.

### 7.2.5 Patients initiating dialysis during the treatment period

In patients judged on clinical grounds to require dialysis during the study, study medication will be continued until study closure, unless protocol specified reasons for investigational product discontinuation are present. See Section 7.7.4 for criteria for rescue therapy in dialysis patients. Initiation of dialysis should be recorded in the eCRF.

### **7.3 Labelling**

Labelling of the investigational products will be carried out by AstraZeneca or their designee in accordance with current Good Manufacturing Practice (GMP). The labels will fulfil GMP Annex 13 requirements for labelling and local regulatory guidelines. Label text will be translated into local language.

### **7.4 Storage**

All study drugs should be kept in a secure place under appropriate storage conditions. The investigational product label on the bottle specifies the appropriate storage.

### **7.5 Compliance**

The administration of all study drugs (including investigational products) should be recorded in the appropriate sections of the eCRF.

### **7.6 Accountability**

The study drug provided for this study will be used only as directed in the study protocol.

The study personnel will account for all study drugs dispensed to and returned from the patient. Study site personnel, if applicable or the AstraZeneca monitor will account for all study drugs received at the site, unused study drugs and for appropriate destruction. Certificates of delivery, destruction and return should be signed. Unused and/or returned investigational products should be destroyed according to local regulations.

### **7.7 Concomitant and other treatments**

#### **7.7.1 Concomitant medications**

Concomitant medications are any prescription or over-the-counter preparations, including herbal products and “natural remedies”, used by a patient while participating in this clinical study. For all concomitant medications, an indication for its use should be provided. If the stated indication is a non-specific condition, e.g. “rash”, documentation of the condition, as specific as possible, should be maintained in the patient’s clinical study records as source documentation.

##### **7.7.1.1 Statins**

When coadministered with roxadustat, hydroxymethylglutaryl coenzyme A reductase inhibitor (statin) exposure was increased 2- to 3-fold. Investigators should consider this interaction and local prescribing information when deciding on the appropriate statin dose for individual patients, bearing in mind the impact of ethnicity, other concomitant medications, renal and hepatic function. Goals of lipid lowering treatment should be maintained as clinically indicated. The recommended maximum daily statin doses are: simvastatin 20 mg, atorvastatin 40 mg, rosuvastatin 10 mg, pravastatin 40 mg, fluvastatin 40 mg (20 mg if eGFR<30), pitavastatin 2 mg (1 mg if eGFR<30).

### **7.7.1.2 Phosphate binders**

When coadministered with phosphate binders, roxadustat exposure was reduced. Patients should be advised to discuss with the investigator before changing their phosphate binder dose or dosing time. To optimize absorption of roxadustat, subjects should take roxadustat with at least 1 hour separation from their phosphate binder.

### **7.7.1.3 Herbal medicines**

Use of herbal medicine during the study is not prohibited but strongly discouraged. All herbal and natural remedies should be reviewed by the investigator and if considered safe, may be allowed to continue at the same dose.

## **7.7.2 Prohibited medications**

The following medications/therapies are prohibited during the study:

- Any other investigational drug: from randomization until EOS
- Any erythropoietin analogues during the treatment period, except as rescue medication (Section 7.7.4.3)
- Iron-chelating agents (e.g. deferoxamine/desferrioxamine, deferiprone or deferaxirox therapy): from 4 weeks prior to screening until EOS
- Androgens: from randomization onwards until EOS
- Dapsone (at any dose) from randomisation to EOS
- Chronic doses of acetaminophen/paracetamol >2.0 g/day from randomization until EOS

## **7.7.3 Supplemental iron use**

Oral iron supplementation is allowed for both treatment arms without restriction.

Oral iron is recommended for dietary supplementation to support erythropoiesis and as the first-line for prevention and treatment of iron deficiency, unless the patient is intolerant to this treatment.

In addition to scheduled assessments (Table 1), iron indices may be assessed anytime (via central lab) to evaluate iron storage status of the patients, if considered necessary by the investigator.

## **7.7.4 Rescue therapy guidelines**

Rescue therapy guidelines are provided to optimize standardization of the use of rescue therapy by investigators and to ensure safety of the individual study patients. Rescue therapy should be recorded in the eCRF.

#### 7.7.4.1 Intravenous iron supplementation

The use of intravenous iron is not encouraged in the setting of this placebo-controlled study. Oral iron is recommended for dietary supplementation to support erythropoiesis and as the first-line for prevention and treatment of iron deficiency, unless the patient is intolerant to this treatment.

The investigator may initiate the use of an approved IV iron supplement if:

- the patient is receiving or does not tolerate oral iron, **and**
- Hb < 8.5 g/dL **and**
- Ferritin <100 ng/ml **or** Transferrin saturation (TSAT) <20%

Study treatment may continue during IV iron administration. Ferritin and TSAT assessment is recommended 4 weeks after IV iron administration. Discontinuation of IV iron supplementation is recommended once the patient is no longer considered to be iron deficient (ferritin  $\geq$ 100 ng/mL and TSAT  $\geq$ 20%) or Hb >9 g/dL, whichever comes first. Use of IV iron will be recorded in the eCRF.

#### 7.7.4.2 Red blood cell transfusion

Red blood cell (RBC) transfusion is allowed if rapid correction of anemia is required to stabilize the patient's condition (e.g. acute hemorrhage) or the investigator is of the opinion that the blood transfusion is a medical necessity. Study drug treatment may continue during or after RBC transfusion administration. Transfusion will be recorded in the eCRF.

#### 7.7.4.3 Initiation of Rescue with an approved erythropoietin analogue

The investigator may initiate use of an approved erythropoietin analogue if all of the following criteria are met:

- A patient's Hb level has not sufficiently responded to two or more dose increases or the maximum dose limit of the study drug has been reached, **and**
- The patient's Hb is <8.0 g/dL on two consecutive measurements drawn at least five days apart; **and**
- Clinical judgment does not suggest iron deficiency or bleeding as a cause of lack of response or rapid decline in Hb (see 7.7.4.1 and 7.7.4.2 above for addressing these conditions), **and**
- Reducing the risk of alloimmunization in transplant eligible patients and/or reduction of other RBC transfusion-related risks is a goal

The patient is not allowed to be administered both erythropoietin analogue and study drug at the same time. For patients not on dialysis, treatment with erythropoietin analogue should be

stopped when Hb >9 g/dL or after a 4-week cycle has been completed, whichever comes first. Study treatment should be resumed after the following intervals:

- Two days after stopping epoetin
- One week after stopping darbepoetin alfa
- Two weeks after stopping methoxy polyethylene glycol-epoetin beta (Mircera)

Use of erythropoietin analogues will be recorded in the eCRF.

Patients may receive 2 cycles of rescue with erythropoietin analogues. If they meet the above criteria for erythropoietin rescue for a third time, study drug should be permanently discontinued (see Section 3.9.3). Study drug should be permanently discontinued for subjects who initiate dialysis and who are clinically judged to require erythropoietin analogue therapy.

#### **7.7.4.4 Therapeutic Phlebotomy**

If there are clinical concerns for a patient due to excessive elevation in Hb levels, the investigator may decide to perform a therapeutic phlebotomy instead of, or in addition to, a dose hold. This should be documented and discussed with the study AstraZeneca study physician.

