### **1.3 Benefit/risk and ethical assessment**

The primary benefit for patients randomized to roxadustat is expected to be the correction of anemia, including the relief of associated signs and symptoms and an improved quality of life. Roxadustat is expected to be at least as safe as parenteral erythropoietin analogues.

Patients treated with placebo may not obtain any benefit in terms of anemia correction, but may benefit from the closer follow-up and will receive alternative therapies whenever clinically indicated.

An established dose adjustment algorithm will be used during the study to titrate roxadustat doses to enable patients to achieve and maintain Hb levels, while closely monitoring the rate of rise of Hb levels. Roxadustat doses may be held and therapeutic phlebotomy is allowed in the event of excessive erythropoiesis.

In studies with healthy subjects, headache and dizziness were common events, which occurred at a higher frequency with roxadustat compared to placebo. An increased frequency of mild to moderate musculoskeletal pain was also noted with high doses of roxadustat. These findings were not observed at the usual therapeutic dose range in the Phase 2 studies in the target populations.

Treatment with roxadustat was associated with increases in heart rate which were most pronounced at supra-therapeutic doses (5 mg/kg). At the high clinical dose of 2.75 mg/kg, the increase was modest (about 10 bpm from baseline, placebo corrected). In the Phase 2 studies, there were no adverse effects on hemodynamics with repeated dose administration in the therapeutic dose range. The cumulative safety data to date have not identified any major risks related to roxadustat, which was well tolerated by healthy subjects and patients with CKD.

The safety of treatment with roxadustat and placebo will be carefully monitored and an independent Data Safety Monitoring Board (DSMB) will perform periodic assessments of safety data to detect any potential safety signals that may arise during the study and advise the International Coordinating Investigator and Sponsor accordingly. Based on data so far obtained, treatment with roxadustat is expected to be efficacious in treating anemia in patients with CKD. The safety profile of the compound, together with the safety monitoring implemented would minimize the risk to study participants. The benefit-risk in this study is therefore deemed acceptable.

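### At Hb ≥13.0 g/dL, Section 7.2.4 and Table 4 require a dose hold that Sections 6.7 and 7.7.4.4 let phlebotomy replace, and Table 4 does not say how an Hb fall after phlebotomy is read

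*Protocol*

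**What the plan says.** Five places in the protocol bear on a patient whose Hb has risen too far.

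- **Section 7.2.4.** At a Hemocue Hb of 13.0 g/dL or more, "dosing will immediately be put on hold". The restart rule follows: "Resume dosing at a subsequent visit when Hb ≤11.9 g/dL, at a dose that is reduced by two dose steps".
- **Table 4.** The column for Hb ≥13.0 holds one entry for every row of 4-week change: "Hold, then resume dosing when Hb ≤11.9 g/dL, at a dose that is reduced by two dose steps".
- **Section 7.7.4.4.** Where there are clinical concerns about excessive Hb elevation, "the investigator may decide to perform a therapeutic phlebotomy instead of, or in addition to, a dose hold". The section adds that this is to be documented and discussed with the sponsor's study physician.
- **Section 6.7.** The same permission: "the investigator may decide to perform a therapeutic phlebotomy instead of or in addition to, a dose hold". It does not mention the discussion with the study physician.
- **Section 1.3.** "Roxadustat doses may be held and therapeutic phlebotomy is allowed in the event of excessive erythropoiesis".

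Up to week 52, Table 4 reads the current Hb together with the change over the past 4 weeks. Footnote a drops the 4-week change after week 52 and uses current Hb alone. Sections 7.2.2 to 7.2.4 and Table 4 do not mention phlebotomy.

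**The concern.** Two rules appear to govern the same patient. One makes the hold automatic and ties a two-step reduction to the restart. The other lets the investigator put phlebotomy in place of a hold and does not say whether the reduction still applies.

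The next dose review then raises a second question. Phlebotomy lowers Hb by removing blood, and Table 4 has no exception for that. Read literally, it treats the fall like any other, and in some cells a fall of more than 1.0 g/dL shifts the instruction upward.

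What is at stake is the dose after an Hb overshoot. Section 6.7 relies on the dose algorithm to limit excessive Hb elevation, and contributing cardiovascular safety data is the primary safety objective (Section 2.1). Exposure after an overshoot should not depend on which section a site happens to read.

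**Working it through.** **1. Does the phlebotomy wording refer to the hold at 13.0 g/dL?** Sections 1.3, 6.7 and 7.7.4.4 do not name that value. The holds and reductions in the dosing rules are:

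- Hb ≥13.0 g/dL: hold (7.2.4, Table 4).
- Excessive erythropoiesis, a rise of more than 2.0 g/dL within 4 weeks: one step down, not a hold (Table 4, 7.2.3).
- Interruptions under 3.9.1: for prohibited medication or erythropoietin analogue rescue, not for high Hb.

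The first is the only hold that the dosing rules attach to an Hb value. The permission to replace a hold therefore has no other hold to refer to.

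**2. Reproduce the protocol's own dose examples.** "Dose increases (↑) and reductions (↓) are pre-set according to dose steps": 20, 40, 50, 70, 100, 150, 200, 250, 300 mg. One step up from 70 mg is 100 mg, and one step down from 150 mg is 100 mg. Both match the examples under Table 4.

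**3. Apply the rules after a reading ≥13.0 g/dL.** For the third column, assume phlebotomy replaced the hold and the reading ≥13.0 is the 4-week comparator. If the next Hb is ≤11.9, the fall is at least 13.0 − 11.9 = 1.1 g/dL, so the row for a fall of more than 1.0 always applies.

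| Next Hb (g/dL) | Hold route (7.2.4) | Phlebotomy without hold, up to week 52 | Phlebotomy without hold, after week 52 |
|---|---|---|---|
| ≥13.0 | still on hold | hold | hold |
| 12.0–12.9, fall ≤1.0 | still on hold | one step down | one step down |
| 12.0–12.9, fall >1.0 | still on hold | no change | one step down |
| 10.5–11.9 | restart two steps lower | one step up | no change |
| <10.5 | restart two steps lower | one step up | one step up |

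Example for the 12.0–12.9 band, starting from 13.5: a next Hb of 12.5 to 12.9 is a fall of at most 1.0 (one step down), and 12.0 to 12.4 is a fall of at least 1.1 (no change).

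Up to week 52, the fall itself changes the instruction in two cells. At 10.5–11.9 a stable Hb would give no change; the fall makes it an increase. At 12.0–12.9 a stable Hb would give a reduction; a fall of more than 1.0 makes it no change.

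**4. Size of the gap at Hb ≤11.9, up to week 52.** Two steps down against one step up is three steps. The maximum is the lower of 3.0 mg/kg or 300 mg, so the higher step needs a body weight of at least dose ÷ 3.0.

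| Dose before (mg) | Hold route (mg) | Phlebotomy route (mg) | Ratio | Weight needed for higher step (kg) |
|---|---|---|---|---|
| 70 | 40 | 100 | 2.5 | 33.3 |
| 100 | 50 | 150 | 3.0 | 50.0 |
| 150 | 70 | 200 | 2.9 | 66.7 |
| 200 | 100 | 250 | 2.5 | 83.3 |
| 250 | 150 | 300 | 2.0 | 100.0 |

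After week 52, at Hb 10.5–11.9, the gap is two steps (from 150 mg: 150 mg against 70 mg).

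**5. Sensitivity to the comparator.** Visits are every 2 weeks to week 20, while dose reviews are every 4 weeks. Suppose Hb is 12.0 at a review, 13.0 two weeks later with phlebotomy, and 11.8 at the next review. The 4-week change is 11.8 − 12.0 = −0.2, and Table 4 gives no change. If the reading of 13.0 is itself the comparator, the change is −1.2 and Table 4 gives an increase.

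**The case against.** The strongest reply is that 6.7 and 7.7.4.4 only permit. A site that always follows 7.2.4 breaches neither, and their trigger is clinical concern rather than a stated Hb value. Section 1.3 also links holds and phlebotomy to excessive erythropoiesis, which Table 4 defines by rate of rise and handles separately from Hb ≥13.0. That is fair as far as it goes: the link to 13.0 g/dL is an inference. But excessive erythropoiesis calls only for a one-step reduction, so a permission to replace a hold still has to mean the hold in 7.2.4. A permission to omit a step that another section makes automatic is a conflict.

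A second reply is that 7.7.4.4 brings in the study physician. This makes an unintended dose increase less likely. It supplies no rule for the dose afterwards, and 6.7 does not repeat it.

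A reader might also infer more than the documents support:

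- **That the dose is always raised after phlebotomy.** It is not. Away from Hb <10.5, the increase needs week 52 or earlier, a comparator more than 1.0 g/dL above the next reading, and a next Hb ≤11.9. That Table 4 counts a phlebotomy fall at all is inferred from the lack of an exception.
- **That nearly all patients concerned are on roxadustat.** The protocol gives no split by arm.
- **That patients are escalated while in the range linked to cardiovascular harm.** The increase arises at Hb ≤11.9, below that range. The remark in 1.2.3 about levels above 13 g/dL stands in a discussion of erythropoietin analogues, and the section goes on to say that roxadustat acts by a different mechanism.
- **That the cardiovascular data are compromised.** Without the frequency of phlebotomy, no such effect can be sized.

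**Conclusion.** The point holds as a conflict between rules. The hold at Hb ≥13.0 g/dL and its two-step restart reduction are unconditional in 7.2.4 and Table 4, but replaceable under 6.7 and 7.7.4.4 and optional in the wording of 1.3. The conflict over the hold runs through the whole treatment period.

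The sharpest consequence is conditional. Up to week 52, with the reading ≥13.0 as the 4-week comparator and a next Hb ≤11.9, the two routes end three dose steps apart, a 2- to 3-fold difference for prior doses of 70 to 250 mg where the weight cap allows. At 12.0–12.9 the phlebotomy route gives one step down or no change while the hold route is still off drug. After week 52 the gap at 10.5–11.9 is two steps.

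The number of patients affected cannot be estimated from the protocol. Version 6.0 is dated 31 August 2018 and the study was expected to end by Q3 2018, so little dosing may remain under it. Which clinical rule is right is not judged here.

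**What to change.** Reconcile Sections 1.3, 6.7, 7.2.4 and 7.7.4.4 and Table 4 so that they agree on two things:

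1. whether the hold at Hb ≥13.0 g/dL and its restart reduction still apply when phlebotomy is done;
2. how a 4-week Hb change that spans a phlebotomy is read at the next dose review.

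Program IWRS to match. The choice of rule is the sponsor's.

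The cost is amendment wording in five places and a phlebotomy flag in IWRS. No extra visits or patients are needed.
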